**ABBREVIATIONS:**

NSCLC: Non-small cell lung cancer

EBUS: endobronchial ultrasound

ROSE: Rapid on-site cytopathologic examination

CT: computed tomography

DLT: dose limiting toxicity

MTD: maximum tolerated dose

MTV: maximum tolerated volume

CTCAE: Common Terminology Criteria for Adverse Events

## **1. SYNOPSIS:**

### **TITLE: A PHASE I TRIAL OF INTRATUMORAL CISPLATIN FOR EARLY STAGE, RESECTABLE, NON-SMALL CELL LUNG CANCER**

#### **RATIONALE:**

Non-small cell lung cancer (NSCLC) is the leading cause of cancer-related death in the United States. Even for early stage disease, the rate of recurrence following surgical resection is as high as 50%. Although neoadjuvant therapy, administered before surgery, for early stage lung cancer is associated with a survival benefit, it is rarely used due to the systemic toxicity of intravenous (IV) cytotoxic chemotherapy. IV immunotherapies are also being evaluated in combination with systemic therapies in the neoadjuvant setting. However, only a minority of patients respond to immunotherapy. One of the most common reasons for failure of immunotherapy is lack of presentation of tumor antigens to the immune system, a problem that may be potentially addressed with cytotoxic agents.

Over the last several years, case series have demonstrated the feasibility and safety of delivering cisplatin directly into lung tumors. For patients that have recurrent lung cancer in a previous radiation field, our prior work demonstrated that a series of four injections results in a 71% complete or partial response rate based on RECIST criteria of the treated volume. The only toxicity seen in this series was nausea and/or vomiting. Further, there are in vitro data that support the idea that cisplatin may modulate the immune system.

Given the current knowledge of safety and tolerability of intratumoral cisplatin, coupled with the potential to achieve immune priming that may help address systemic micrometastases, have led us to postulate that intratumoral cisplatin is a well-tolerated, and potentially effective, neoadjuvant therapy for patients with early stage, resectable, non-small cell lung cancer.

#### **PRIMARY OBJECTIVE:**

To identify the maximum tolerated dose (MTD) of intratumoral cisplatin, delivered during a single bronchoscopy with cone-beam CT confirmation, in a dose escalation protocol

**DESIGN:** 3+3 dose escalation. The amount of delivered cisplatin is based on the volume of the tumor being treated, beginning at a volume of cisplatin of 1/4th the volume of the tumor.

## 2. BACKGROUND:

2.1. **Study Disease:** Non-small cell lung cancer (NSCLC) is the leading cause of cancer-related death in the United States. Even for tumors that are identified at an early stage and resected, the rate of recurrence may be as high as 50%. Direct intratumoral (IT) delivery of cisplatin into early stage lung cancers at the time of diagnosis has several clear potential benefits. First, it reduces time to treatment from time of diagnosis, potentially improving outcomes through this mechanism alone. Second, intratumoral delivery of cisplatin may provide the benefits of intravenous (IV) neoadjuvant chemotherapy while minimizing the systemic, off-target toxicities that have limited the adoption of this approach. Finally, there is increasing evidence that chemotherapy induced tumor cell death may “prime” the immune system by allowing immune effector cells to recognize tumor epitopes and kill undetected micrometastatic tumor cells beyond the resection specimen.

### 2.2. **Rationale:**

**NSCLC Commonly Results in a Prolonged Diagnosis to Treatment Time:** Lung cancer remains one of the most challenging diseases to diagnose, stage, and treat. Patients generally undergo CT scans, PET-CT scans, and MRIs to determine the stage and extent of a potential or confirmed NSCLC. This can result in prolonged times to surgical resection. In fact, diagnosis to surgical resection times greater than 8 weeks appear to occur in approximately 30% of patients, and are independently associated with stage progression and a decreased median survival. In a highly homogenous group of patients with Stage 1 squamous cell carcinoma, delayed surgery (>38 days) was associated with a worse overall survival. Initiating therapy earlier has the potential to improve outcomes for patients with early stage NSCLC.

**Neoadjuvant Therapy for Resectable Lung Cancer is Effective but Rarely Performed:** In early-stage, resectable, lung cancer, neoadjuvant chemotherapy improves survival, with a 13% reduction in the relative risk of death. The majority of neoadjuvant chemotherapy trials have utilized IV cisplatin, or a closely related drug, carboplatin. However, neoadjuvant IV chemotherapy results in significant rates of adverse effects. For instance, neoadjuvant cisplatin plus gemcitabine results in a 32% rate of systemic hematologic toxicity. Intratumoral therapy, delivered at the time of diagnosis, has the potential to immediately initiate therapy and capture the benefits of neoadjuvant chemotherapy while minimizing systemic toxicity.

**“Priming” the Immune System May Facilitate Immune Mediated Tumor Destruction:** In 2015, the first immunotherapy drug for lung cancer was approved for the treatment of NSCLC. Nivolumab is a humanized antibody that binds the programmed death ligand 1 (PD-L1), one of several immune checkpoint inhibitors (ICIs), that prevent tumor-mediated downregulation of cytotoxic T lymphocytes (CTLs). Nivolumab demonstrated a significant increase in median overall survival compared to docetaxel for patients with advanced squamous NSCLC. This median difference was driven by a significantly prolonged survival in the 20% of patients who responded. Similarly, the ICIs pembrolizumab and durvalumab result in response rates of 45% in treatment-naïve advanced NSCLC and 28% in locally advanced non-resectable NSCLC, respectively. Within each of these studies, there are groups of patients that experienced durable and

prolonged NSCLC remissions.

The impressive results achieved for a minority of patients with NSCLC have led to considerable interest in additional mechanisms of immune modulation. Some of the most notable ICI responses in fact have occurred in melanoma and lung cancer. These are considered carcinogen-driven cancers with high rates of human tumor-specific peptides that arise from somatic mutations in the cancer genome. One reason for failure of ICI therapy is lack of presentation of these antigens to the immune system. This may lead to a relative absence of CTLs in the tumor microenvironment and is associated with failure of ICI therapy. One mechanism for recruiting immune effector cells is tumor cell death which can be induced by cytotoxic agents or radiation.

### 2.3. **Investigational Agent:**

**Cisplatin Delivered IV is Highly Toxic:** One of the most commonly used IV cytotoxic medications for the treatment of lung cancer is cisplatin. Cisplatin binds to DNA, cross-linking strands and thereby inhibiting mitosis, which in turn leads to apoptosis of the tumor cell. However, it has more recently been recognized that cisplatin may have immunomodulatory effects that extend beyond those related merely to cell death. In vitro studies implicate cisplatin in upregulation of the major histocompatibility complex (MHC class 1), recruitment and proliferation of effector cells, upregulation of the activity of cytotoxic effector cells, and downregulation of the immunosuppressive environment. Specifically, cisplatin appears to increase recruitment of CTLs and to upregulate Fas receptor, a death signal. Importantly, there is also evidence that cisplatin may work synergistically with PD-1 inhibitors. Although many standard regimens for the treatment of NSCLC include an IV platinum agent, this delivery approach is complicated by significant toxicity. Systemic IV cisplatin is associated with greater than 40 untoward effects; the most common is nephrotoxicity, but may commonly include gastrointestinal, hematologic, cardiac, and hepatic events. These off-target effects greatly impair patient quality of life and tolerance of the drug, which in turn limits the dose and frequency at which the medication can be given. In fact, for Stage IV NSCLC there is evidence that platinum-based chemotherapy may hasten death compared to palliative care. **The FDA guidance document for cisplatin highlights a feature of this drug that is atypical for chemotherapeutics, namely that it is more highly absorbed in normal tissues versus tumor tissue.** Direct intratumoral (IT) delivery thus has the potential to maximize the therapeutic effect of cisplatin while minimizing off-target adverse effects.

**Safety of IT Cisplatin in Prior Clinical Studies:** There is accumulating evidence that cisplatin may be safely delivered directly into a lung tumor with minimal side effects. In general, intratumoral injection for lung cancer dates back to at least 1978. The first Phase III trial of a bronchoscopically delivered agent, the Bacillus Calmette-Guerin vaccine, was completed in 1986. This study established the safety of IT delivery via a needle into early stage lung cancers but did not demonstrate significant clinical effect. The development of modern technologies such as endobronchial ultrasound, navigational bronchoscopy, robotic bronchoscopy, and intraoperative cone-beam CT scan has resulted in the ability to precisely deliver an agent into a tumor, and the opportunity to synergistically augment the effect of modern therapies.

In 2006, Celikuoglu et al used intratumoral injection of a maximum dose of 40mg of cisplatin through a flexible bronchoscope for patients with obstructive, inoperable NSCLC. This same group also performed bronchoscopic injection of cisplatin into centrally located, early-stage lung cancers. They demonstrated endobronchial regression of tumor which enabled subsequent surgical resection. Intratumoral cisplatin has subsequently been used in multiple other studies at doses of 30-40mg. In a Phase III clinical trial, 4 patients with limited-stage small cell lung cancer (SCLC) received intratumoral cisplatin at a dose of 40mg (ClinicalTrials.gov Identifier: NCT01487499). There were insufficient numbers of patients to assess for the primary outcome of progression-free survival, but no reported adverse effects. Our group has utilized intratumoral cisplatin for treatment of late stage disease at a maximum injected dose of 40mg, with only nausea and vomiting identified as adverse effects. At these doses, there appears to be significant efficacy with a 71% complete or partial response rate based on data from two centers (manuscript accepted to the Journal of Thoracic Oncology). We have preliminary data using flow cytometric analyses of lesions sampled 1 week after intratumoral cisplatin administration of cisplatin at these doses that demonstrate up to 90% cell death in the treated volume. Intratumoral cisplatin in the range of 40mg can result in detectable platinum blood levels following administration. Nausea and vomiting were also the most common adverse events documented in a larger series of 36 patients. Serious adverse events have been reported when IT cisplatin is combined with other therapies. Bronchomediastinal fistula has occurred when IT cisplatin was delivered concomitantly with re-irradiation. Similarly, organizing pneumonia occurred in a patient who was simultaneously receiving intravenous cisplatin. Full details of prior studies have been included in the Summary of Prior Human Studies.

**Delivery of IT Cisplatin:** Despite series demonstrating the overall safety of intratumoral cisplatin, there has been little systematic investigation of the optimal dose or delivery location. For instance, in many studies an identical dose of 40mg of cisplatin has been delivered, regardless of morphology or other tumor characteristics. Further, intraoperative imaging has not been evaluated to guide or assess IT delivery. **It is therefore critical to establish a safe dose for intratumoral cisplatin in a prospective study in patients with early stage resectable NSCLC with appropriate assessment for dose limiting toxicity (DLT).**

**Rationale for Dosing:** Prior studies have generally treated large tumors (>3cm diameter) and focused on using a fixed dose of cisplatin. However, for smaller tumors the delivery volume of the agent (1mg/ml concentration) may result in reaching the maximum tolerated volume before reaching the MTD. For instance, a 2 cm diameter tumor would have a volume of approximately 4 mL (assuming a spherical morphology). It is clear that delivering a 40mg dose (40mL) is not feasible in this setting. The additional variance of tumor size in this study motivated further analysis to determine feasibility of alternative dosing strategies for smaller tumor volumes. We evaluated 28 cases of patients with recurrent lung cancer in a previously radiated field treated with intratumoral cisplatin at the University of Vermont and the University of Florida. We applied our published computational model of intratumoral cisplatin pharmacokinetics to evaluate a volumetric

dosing strategy. This series include tumors less than 3 cm in diameter, many of which empirically received a lower dose of cisplatin. Each case was evaluated for response using RECIST criteria, v1.1. This model was used to simulate the percentage of tumor cells that reach the threshold intracellular concentration of cisplatin required for cell death (Fig 1). These results demonstrate robust distribution of the agent, and associated cytotoxicity, across a broad range of smaller tumors. For instance, a 4 cm diameter tumor is approximately 30 cm^3 in volume. Delivering one-half of the tumor volume in total drug volume, with a 1/mg/ml concentration, results in a 15mg dose of delivered cisplatin, which would be predicted to lead to cytotoxicity to over 90% of the tumor.

The second consideration for dosing in the current study is the maximum administered dose. The majority of prior series have not used doses above 40mg. In our open Phase 1A study of intratumoral cisplatin for metastatic NSCLC, the 20mg dose cohort did not result in any dose limiting toxicity and we are moving to the 40mg dose cohort. Thus, for this protocol we consider 40mg to be the maximum dose. We have outlined three dosing cohorts in the protocol: an Initial cohort at 1/4th tumor volume, a De-escalation cohort at 1/8th tumor volume, and an Escalation cohort at 1/2 tumor volume. If we reached the Escalation cohort (1/2 volume) the maximum dose delivered would be 32.8mg. Tables detailing example doses for each cohort have been included in Section 4.

### 3. PATIENT SELECTION

#### 3.1. Inclusion criteria

3.1.1. Age  $\geq$ 18 years.

3.1.2. ECOG performance status 0 or 1

[figure not shown]
3.1.3. Patients must have adequate organ and marrow function as defined below:

3.1.3.1. Leukocytes  $\geq$ 3,000/mcL

3.1.3.2. Platelets  $\geq$ 100,000/mcL

3.1.3.3. Total bilirubin  $\leq$  institutional upper limit of normal (ULN)

3.1.3.4. AST(SGOT)/ALT(SGPT)  $\leq$ 3  $\times$  institutional ULN

**Figure 1: Dosing of Cisplatin Based on Tumor Volume.** Isodose lines demonstrate robust coverage of small tumors with low doses of intratumoral cisplatin (1mg/ml). For reference, a 10 cm^3 volume corresponds to a 2.7 cm diameter tumor (assuming a spherical morphology).

- 3.1.3.5. Creatinine  $\leq$  institutional ULN
- 3.1.4. Patients with a prior or concurrent malignancy whose natural history or treatment does not have the potential to interfere with the safety or efficacy assessment of the investigational regimen are eligible for this trial
- 3.1.5. Have known or suspected clinical stage I-IIb NSCLC after CT and/or PET\_CT at time of enrollment
- 3.1.6. Presence of a target lesion with a minimum volume of 1.0 cm^3, (approximately 1.2 cm in diameter) and  $\leq$  5.0 cm in diameter
- 3.1.7. Agreement from a cardiothoracic surgeon, following review of past medical history, medications, pulmonary function testing, and CT scan that patient is likely to be a surgical candidate and that, after considering known possible adverse events, delivery of intratumoral cisplatin is unlikely to adversely affect surgical feasibility
- 3.1.8. Rapid on-site cytopathologic examination (ROSE) performed during the procedure returns likely NSCLC (per the determination of a trained, attending, cytopathologist). No research procedures will be performed if ROSE is non-diagnostic
- 3.1.9. A CT scan of the chest (with or without contrast) within 1 month of the screening visit
- 3.1.10. Ability to understand and the willingness to sign a written informed consent document

### 3.2. **Exclusion criteria**

- 3.2.1. Use of an investigational agent within 30 days of the screening visit
- 3.2.2. IV chemotherapy within the 30 days of the screening visit
- 3.2.3. Pregnancy/lactation (pregnancy test to be performed by pre-op as part of standard of care for women of child-bearing age as defined by UVMMC Policy NPREP16)
- 3.2.4. History of prior radiation to the study lesion
- 3.2.5. History of allergic reaction to cisplatin or its derivatives
- 3.2.6. Patients with uncontrolled intercurrent illness
- 3.2.7. Physician determination that patient would not be appropriate for study

## 4. **TREATMENT PLAN**

### 4.1. **Agent Administration**

4.1.1. Treatment will be administered intraprocedurally. Reported adverse events and potential risks are described in the Data and Safety Monitoring Plan. No investigational or commercial agents or therapies other than those described below may be concomitantly administered with the intent to treat the patient's malignancy.

4.1.2. The agent will be administered at 3 potential dose levels in a 3+3 design.

4.1.3. IT cisplatin 1mg/ml will be dosed with a delivered volume based on a proportion of the volume of the tumor.

4.1.4. This volumetric dosing approach is being employed to account for the dramatic tumor volume differences seen in this diameter range. Prior studies have most commonly used an empirically derived intratumoral dose of 40mg or less (although have ranged to 100mg intratumorally, Appendix B). To minimize the risk of extravasation of the agent from small tumors we have adopted a volumetric dosing strategy.

4.1.4.1. First dose cohort: The delivered quantity of cisplatin will equal one-fourth (1/4th) of the total tumor volume.

4.1.4.2. De-escalation dose cohort : The delivered quantity of cisplatin will equal one-eight (1/8th) of the total tumor volume This dose cohort will only be used if the 1/4-tumor volume dose cohort is terminated due to DLT.

4.1.4.3. Escalation dose cohort: The delivered quantity of cisplatin will equal one-half (1/2) of the total tumor volume

4.1.4.4. Lower or higher dose cohorts may be pursued if indicated based on the rate of DLT, pending formal review and approval by the appointed Data Safety Monitoring Committee of the UVM Cancer Center. This is a standard approach since the DSMC reviews all AEs and relevant data at any change in dose level (pre-specified or otherwise) before preceding to the next dose level.

4.1.5. Tumor volume will be determined using automated segmentation available in the open-source software platform (<https://chestimagingplatform.org>) and manually verified.

4.1.6. The minimum volume that is feasible to deliver is 0.5mL.

4.1.7. This leads to the following “INITIAL” *example* dosing regimen for tumors of a specified volume, beginning at 1/4th Volumetric Dosing and assuming that < 2 of the first 3 participants have a dose limiting toxicity (DLT), defined as a Grade 3 by the CTCAE v5.0:

Example Tumor Volume(mL)*	Approximate Tumor Diameter (cm)*	INITIAL		First Dose Cohort:	
		First Dose Cohort: 1/4 Tumor Volume (mL)	Delivered Volume (mL)	IT Cisplatin	Total Cisplatin (mg)
				Not Eligible**	
1.2	1.3	0.3			
1.8	1.5	0.5		0.5	0.5
4.2	2.0	1.1		1.1	1.1
8.2	2.5	2.1		2.1	2.1
14.1	3.0	3.5		3.5	3.5
22.5	3.5	5.6		5.6	5.6
33.5	4.0	8.4		8.4	8.4
47.7	4.5	11.9		11.9	11.9
65.5	5.0	16.4		16.4	16.4

\*Calculated based on volume of a sphere  
\*\*Minimum delivery volume is 0.5mL

4.1.8. The following are *example* doses for the DE-ESCALATION cohort:

Example Tumor Volume(mL)*	Approximate Tumor Diameter (cm)*	DE-ESCALATION		 Second Dose Cohort: IT Cisplatin Delivered Volume (mL)	Total Cisplatin (mg)	
		Second Dose Cohort: 1/8 Tumor Volume(mL)	Delivered Volume (mL)			
			Not Eligible**			
1.2	1.3	0.2				
1.8	1.5	0.2		Not Eligible**		
4.2	2.0	0.5		0.5	0.5	
8.2	2.5	1.0		1.0	1.0	
14.1	3.0	1.8		1.8	1.8	
22.5	3.5	2.8		2.8	2.8	
33.5	4.0	4.2		4.2	4.2	
47.7	4.5	6.0		6.0	6.0	
65.5	5.0	8.2		8.2	8.2	

\*Calculated based on volume of a sphere  
\*\*Minimum delivery volume is 0.5mL

4.1.9. The following are *example* doses for the ESCALATION cohort:

Example Tumor Volume(mL)*	Approximate Tumor Diameter (cm)*	ESCALATION			Second Dose Cohort Total Cisplatin (mg)
		Second Dose Cohort: 1/2 Tumor Volume(mL)	Second Dose Cohort	Total Cisplatin (mg)	
1.2	1.3	0.6	0.6	0.6	0.6
1.8	1.5	0.9	0.9	0.9	0.9
4.2	2.0	2.1	2.1	2.1	2.1
8.2	2.5	4.1	4.1	4.1	4.1
14.1	3.0	7.1	7.05	7.05	
22.5	3.5	11.3	11.3	11.3	
33.5	4.0	16.8	16.8	16.8	
47.7	4.5	23.9	23.9	23.9	
65.5	5.0	32.8	32.8	32.8	

\*Calculated based on volume of a sphere

\*\*Minimum delivery volume is 0.5mL

4.1.10. Dose escalation will be performed as follows:

Number of Patients with DLT at a Given Dose Level	Escalation Decision Rule
0 out of 3	Enter 3 patients at the next escalation dose.
$\geq 2$	Dose escalation will be stopped. This dose level will be declared the maximally administered dose (highest dose administered). Three (3) additional patients will be entered at the next lowest dose level if only 3 patients were treated previously at that dose. If this is the first dose evaluated, a lower dose level will be established, in concert with DSMC, and 3 patients enrolled to that level.
1 out of 3	
Enter at least 3 more patients at this dose level.
 
 
If 0 of these 3 patients experience DLT, proceed to the next dose level.
 
If 1 or more of this group suffer DLT, then dose escalation is stopped, and this dose is declared the maximally administered dose. Three (3) additional patients will be entered at the next lowest dose level if only 3 patients were treated previously at that dose.
 

$\leq 1$ out of 6 at highest dose level below the maximally administered dose	This will be the recommended phase 2 dose. At least 6 patients must be entered at the recommended phase 2 dose.

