6.2. Criteria for endpoint evaluation

6.2.1. Primary Endpoint: Safety (DLT), as defined by CTCAE v 5.0.

6.2.1.1. Assessment of Adverse Events: The PI will be responsible for evaluating all AEs at the end of the individual patient study period. CTCAE v 5.0 grade 3 or above will be considered a DLT

6.2.1.2. The reporting procedures to be followed are presented in the "CTEP, NCI Guidelines: Adverse Event Reporting Requirements" which can be downloaded from the CTEP web site ([http://ctep.cancer.gov/protocolDevelopment/electronic\\_applications/docs/aeguidelines.pdf](http://ctep.cancer.gov/protocolDevelopment/electronic_applications/docs/aeguidelines.pdf)).

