7.1.2.1. At subject, PI, or study team member request

7.1.2.2. If the subject had a Serious Adverse Event (SAE) deemed related to study  
Other: specify

7.1.2.3. During the bronchoscopy, bleeding >100mL or concern for a patient's ability to continue to tolerate the bronchoscopy would result in stopping that procedure (regardless of whether cisplatin had been delivered into the tumor or not). No further intratumoral delivery would be performed.

7.1.3. Criteria under which THE ENTIRE STUDY would need to be stopped.

7.1.3.1. A 30% or greater rate of possibly related, serious, unanticipated events after 6 patients, will trigger halting of the study and initiate IRB and DSMCC review.

7.1.4. Withdrawals/dropout reporting to the IRB prior to study completion will occur at the IRB annual continuing renewal submission

7.1.5. Plan for management of incidental findings:

7.1.5.1. We do not anticipate incidental findings. The pre-bronchoscopy CT scan is obtained as part of clinical care for all patients undergoing a clinically indicated bronchoscopy. Unanticipated findings on the pre-resection CT will be evaluated as potential AEs.

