## 8. ADVERSE EVENT REPORTING:

Type of Event	To whom will it be reported	Time Frame for Reporting	How to report?
Death of a research subject unless the death is expected (e.g. due to disease progression).	UVMCC DSMC and UVM IRB	DSMC: Within 24 hours IRB: Within 24 hours of knowledge of the event	DSMC: Email IRB: RNI Click form
Serious Adverse Event (SAE), regardless of relatedness of expectedness	UVMCC DSMC. Per IRB policy, unexpected, related SAEs are reported	DSMC: Within 10 working days from the time the study team received knowledge of the event. IRB: 24 hours	DSMC: Email IRB: RNI Click form
Non-serious AEs	UVMCC DSMC and UVM IRB	At quarterly DSMCC report. Annually at IRB Continuing review.	DSMC: Email IRB: Click form

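### After a single treatment-related death, no clause makes further enrolment at the same volume wait for DSMC review

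*Combined protocol and SAP*

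**What the plan says.** **DLT definition.** Section 6.2.1.1: "CTCAE v 5.0 grade 3 or above will be considered a DLT". No attribution is required and grade 5 is not treated separately. Section 4.1.7 words it differently, "defined as a Grade 3 by the CTCAE v5.0", and so does not name grades 4 or 5.

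**Decision table (4.1.10).** With 1 DLT in 3 patients: "Enter at least 3 more patients at this dose level". Then: "If 0 of these 3 patients experience DLT, proceed to the next dose level". The first level is 1/4 of tumor volume and the escalation level is 1/2. A level with at most 1 DLT in 6, just below the maximally administered dose, becomes the recommended phase 2 dose.

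**Study-wide halt (7.1.3.1).** "A 30% or greater rate of possibly related, serious, unanticipated events after 6 patients, will trigger halting of the study". The halt starts IRB and DSMC review.

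**Other safeguards.**
- 4.1.4.4: the DSMC reviews the AE data before any change of dose level.
- Section 8: a death that is not expected is reported to the DSMC and the IRB within 24 hours.
- 6.1.2: enrolment is staggered, each patient being released by the previous patient's 1-week assessment (days 5-9 under 4.3.4.1).
- 7.2.9: the PI reviews AEs after that visit.
- 4.2.2 and 4.2.3: DLTs are adjudicated after the 2-week evaluation, and AEs are followed to resection or day 30, whichever comes first.

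**The concern.** Participants have early-stage disease judged likely to be resectable, so a death caused by the injection would be the gravest outcome this study could produce. The written rules respond to it with a report and a count of one. Unless a second DLT occurs, the table sends more patients to the volume at which the death happened. That volume can still be cleared at 1 of 6, named the recommended phase 2 dose, and expanded under 6.3.1 towards the minimum of 10 patients.

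The gap is one of sequence. Each safeguard covers part of the path, but none makes the next patient at the same level wait for an independent view of the death. What is at stake is the protection of those patients and the credibility of a recommended dose reached this way.

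**Working it through.** **1. The plan's own figure.** Section 6.3.2 gives a maximum of 12 for six patients at each of two levels: 2 × 6 = 12. This reproduces.

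**2. The step in volume.** (1/2) ÷ (1/4) = 2 at every tumor size. For the largest example tumor, 65.5 mL, the tables give 16.4 mg and 32.8 mg.

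**3. Can one death trigger 7.1.3.1?** Smallest k with k/n at or above 0.30:

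| Patients n | One event, 1/n | Events needed |
|---|---|---|
| 6 | 16.7% | 2 (33.3%) |
| 7 | 14.3% | 3 (42.9%) |
| 10 | 10.0% | 3 (30.0%) |
| 11 | 9.1% | 4 (36.4%) |
| 12 | 8.3% | 4 (33.3%) |

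For 8 and 9 patients, 3 are needed. One event is below 30% throughout, and before 6 patients the rule does not operate.

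**4. Patients who could follow a death in patient 1.** Two complete the first cohort, 3 form the expansion and 6 enter the next level: 2 + 3 + 6 = 11 of 12. The first 5 are at the same volume, with no DSMC review required before them. The last 6 come after the 4.1.4.4 review.

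**5. What 6.1.2 does.**
- *Death before the 1-week assessment.* Read literally, the release condition is never met and nobody else may be enrolled. The section does not say whether that is intended, or what would lift the block.
- *Death after that visit but within the AE window.* Patient 2 may already be enrolled. Patient 3 is then released by patient 2's assessment, so the death does not enter the condition at all.

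**6. Chance that the count permits escalation after a death in patient 1.** The other five patients at the level must have no DLT, with probability (1 − p)^5. The DLT risk p is an assumption; the documents give none.
- p = 10%: 0.9^5 = 0.59
- p = 17%: 0.83^5 = 0.39

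**7. Chance that 7.1.3.1 fires at patient 6, given that death.** If the death qualifies, one more qualifying event in five patients suffices: 1 − (1 − r)^5. The rate r is assumed, and every event is taken to be possibly related, serious and unanticipated.
- r = 20%: 1 − 0.8^5 = 0.67
- r = 30%: 1 − 0.7^5 = 0.83

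Steps 6 and 7 use different assumed rates and should not be set against each other. At a common 20%, and counting the same events in both, they are complements: 0.8^5 = 0.33 and 0.67. Either way, patients 2 to 6 have been entered before the rule can act.

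**8. How often a hold would apply.** For an assumed related-death risk q per patient, the chance of at least one death in 6 is 1 − (1 − q)^6. The chance of at least two, the present threshold counting deaths only, is 1 − (1 − q)^6 − 6q(1 − q)^5.

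| q | At least 1 of 6 | At least 2 of 6 |
|---|---|---|
| 2% | 11.4% | 0.6% |
| 5% | 26.5% | 3.3% |
| 10% | 46.9% | 11.4% |

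**The case against.** The strongest reply is that the protocol chose a 3+3 rule, that such a rule counts DLTs as yes or no and tolerates 1 in 6, and that several layers of oversight surround it. Much of this stands, and it rules out stronger readings that someone might take from the table alone.

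- *No clause ever pauses the study for DSMC review.* Not so: 7.1.3.1 halts it and starts IRB and DSMC review once its threshold is met.
- *The volume can be doubled after a death without independent review.* Not so: 4.1.4.4 puts DSMC review before any change of level. The 0.59 in step 6 is the chance that the count permits escalation, not that escalation occurs. The table does not point to 4.1.4.4, which invites the misreading.
- *The DSMC is involved only when the level changes.* Not so: under Section 8 it also receives unexpected deaths within 24 hours, SAEs within 10 working days and other AEs quarterly.
- *6.1.2 offers nothing after an early death.* Read literally it blocks the next enrolment. Its faults are silence on release, and no bearing on a later death.
- *7.1.3.1 has only a 0.34 or 0.58 chance of firing at patient 6.* Those are the chances of at least 2 events in 6 at 20% and 30%, counted from none. Once one qualifying event is assumed, the figures are 0.67 and 0.83.

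The PI's review under 7.2.9 is also real, but it is not independent and carries no hold. The DSMC or IRB might suspend the study unprompted; the plan neither requires that nor makes enrolment wait for it. None of these points closes the same-level gap.

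**Conclusion.** The concern holds for same-level enrolment. A related death is one ordinary DLT, at least 3 more patients are then directed to the same volume if it is the only DLT in the first 3, and no clause makes them wait for the DSMC. One death alone cannot trigger 7.1.3.1 at any size from 6 to 12; that follows from the documents' own figures and needs no assumption.

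If the death is patient 1's, up to 5 further patients at that volume could be entered without a required DSMC review. This supposes that the death falls after the 1-week visit, or that 6.1.2 is not read as a block. The probabilities in steps 6 to 8 rest on assumed risks, independence between patients and, in step 7, every event qualifying. They show scale and are not predictions. Whether a given death would count as unanticipated under 7.1.3.1 is a judgement the documents leave open.

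This is a gap in patient protection that should be closed. It does not make the 3+3 design invalid, and the documents do not support a claim that the volume can be doubled unreviewed.

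**What to change.** Reconcile 4.1.10, 6.1.2, 7.1.3.1 and Section 8:

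1. State in 7.1.3, with a cross-reference from the 1-of-3 row of 4.1.10, that a death judged at least possibly related holds further enrolment until the DSMC and IRB have reviewed it and documented their decision. Whether and how the study continues is left to them.
2. Say in 6.1.2 how the release condition applies when the prior patient dies before the 1-week assessment, and that a later death within the AE window falls under the same hold.
3. In 4.1.10, tie the instruction to move to the next level to the DSMC review in 4.1.4.4.
4. Reconcile the DLT wording of 4.1.7 with that of 6.2.1.1.

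The cost is protocol wording, plus a short accrual pause only if such a death occurs. For an unexpected death, the 24-hour report that would start the review is already required.
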